4 STUDY SCHEDULE

The total study duration for each subject consists of pre-screening, screening, treatment, and follow-up periods. A study flow diagram is presented in [Figure 4-1](#).

- (1) Pre-Screening Period:** A separate Informed Consent Form (ICF) will be used for the pre-screening. The pre-screening period is designed for evaluation of histologically confirmed diagnosis of mTNBC (documented by HER-2 negative, ER<1%, PR<1%) and CCR5 positive expression by Immunohistochemistry (IHC) assay. This assay will be performed in archival tissue from previous biopsy specimens. If archival tissue is not available then, fresh core or excisional biopsy will be done. If patient qualifies, then they will undergo full screening.
- (2) Screening Period:** Screening assessments will commence after obtaining signed informed consent, and will include review of medical and medication history, demographic information and baseline disease characteristics, eligibility evaluation, physical examination, vital signs, height and weight, concomitant medications, electrocardiogram (ECG), tumor imaging assessment, routine serum biochemical, hematologic, urinalysis, serum pregnancy (if applicable). These assessments must be conducted within 28 days of the first treatment visit.
- (3) Treatment Period:** Subjects who meet the eligibility criteria will have completed following evaluations and assessments before receiving treatment: a) review of medical and medication history; b) physical examination, vital signs and documentation of ECOG performance status; c) ECG; d) routine serum biochemical, hematologic, urine pregnancy (if applicable) and urine laboratory assessments. Additionally, a blood sample will be collected prior to treatment administration for CTCs PD-L1/CCR5 and CTC - CAMLs analysis.

Each treatment cycle will consist of 21 days. Leronlimab (PRO 140) will be administered subcutaneously weekly on Days 1, 8, and 15 in combination with carboplatin AUC 5 on Day 1 of each cycle (every 21 days). Day 1 of Cycle 2 begins at Day 22. The study treatment will be administered by a licensed medical professional at clinic site or self-administered by subjects at home.

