Tests and Assessments		Screening Period		Treatment Cycle 1 (21 days)				Treatment Cycle 2 (21 days)				Additional Treatment Cycles				Follow-up Period	
Visit	Day(s)	Pre-Screening Visit [1]	Screening Visit [1]	C1D1	C1D8	C1D15	C2D1	C2D8	C2D15	C3D1	C3D8	C3D15	C4D8	C4D15	EOT	Survival Follow-ups	
				Day 1	Day 8	Day 15	Day 22	Day 29	Day 36								
Window				Within 28 Days from Screening visit	7 (± 1) Days from C1D1 visit	7 (± 1) Days from C1D8 visit	7 (± 1) Days from C1D15 visit	7 (± 1) Days from C2D1 visit	7 (± 1) Days from C2D8 visit	7 (± 1) Days from C3D1 visit	7 (± 1) Days from C3D8 visit	7 (± 1) Days from C3D15 visit	7 (± 1) Days from C4D8 visit				
lerolimab (PRO 140) administration [17]				X	X	X	X	X	X	X	X	X	X	X	X		
Carboplatin administration [18]				X			X				X						
Post Injection Site Evaluation by Investigator [19]				X	X	X	X	X	X	X	X	X	X	X	X		
Injection Site Pain Assessment (VAS) [20]					X	X	X	X	X	X	X	X	X	X	X	X[20]	
Survival status																X	
Concomitant medications				X	X	X	X	X	X	X	X	X	X	X	X	X[23]	
Adverse Events				X	X	X	X	X	X	X	X	X	X	X	X		

Footnotes

- [1] A separate Informed Consent Form (ICF) will be used for the pre-screening. The pre-screening period is designed for evaluation of histologically confirmed diagnosis of mTNBC (documented by HER-2 negative, ER<1%, PR<1%) and CCR5 positive expression by Immunohistochemistry (IHC) assay. This assay will be performed in archival tissue from previous biopsy specimens. If archival tissue is not available then, fresh core or excisional biopsy will be done. If patient qualifies, then they will undergo full screening.
- [2] Informed consent must be obtained prior to patient participation in any protocol-related activities that are not part of routine care.
- [3] A complete review of the subject's past medical history (including all prior anti-tumoral therapy related to breast cancer), past surgeries, and current therapies (medications and non-medications) will be undertaken by the Investigator to check that all inclusion and no exclusion criteria have been met.
- [4] Vital signs include blood pressure, heart rate, respiration rate, and temperature will be measured at clinic visit.
- [5] Weight only
- [6] Symptom-directed physical examination at clinic visits
- [7] A 12-lead ECG will be repeated during the study only if clinically indicated and at the discretion of the treating physician.

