4.3 TREATMENT PERIOD

Subjects who meet all eligibility criteria, as per data gathered from Screening Period are to be treated. All subjects who fail to meet eligibility criteria will be considered screen failure and exit the study without further evaluation

Phase Ib

The dose finding portion of study will follow a “3+3” design. The maximum sample size for this portion of the study is 18 subjects that will be followed by treatment according to the schedule described above starting on Cycle 1, Day 1.

Phase II

The maximum sample size for this portion of the study is 30 subjects that will be followed by treatment according to the schedule described above starting on Cycle 1, Day 1.

During the Phase Ib and Phase II of the study, treatment may continue until one of the following criteria applies:

- Disease progression,
- Intercurrent illness that prevents further administration of treatment,
- Unacceptable adverse event(s), or
- Withdrawal of consent

Each treatment cycle consists of 21 days. Leronlimab (PRO 140) will be administered subcutaneously weekly on Days 1, 8, and 15 in combination with carboplatin AUC 5 on Day 1 of each cycle (every 21 days). Day 1 of Cycle 2 begins at Day 22.

4.3.1. Treatment Cycle 1, Day 1

The following assessments will be performed at the first treatment visit of Cycle 1:

- Concomitant medications assessment (see [Section 7.5](#)),
- Vital Signs and body weight measurement (see [Section 7.6](#)),
- Physical examination, including evaluation of all body systems (see [Section 7.7](#))
- ECOG Performance Status (see [Section 7.8](#))

- 12-lead Electrocardiogram (see [Section 7.9](#))
- Collection of lab specimens (see [Section 7.11](#)) for
 - Complete blood count
 - Biochemistry
 - Urine pregnancy test, for female subjects of childbearing potential.
 - Urine sample for urinalysis parameters
 - CTCs PD-L1/CCR5 analysis
 - CTC and CAMLs analysis

Note: Complete blood count, biochemistry and urinalysis can be performed within 3 days prior to each cycle start.

- Leronlimab (PRO 140) Administration (see [Section 6.1.3](#))
- Carboplatin Administration (see [Section 6.2.5](#))
- Post Injection Site Evaluation (performed by Investigator) (see [Section 7.13](#))
- Toxicity assessment (see [Section 7.10](#)) and Review of Adverse Events (see [Section 9](#))

4.3.2. Treatment Cycle 1, Day 8 & Day 15

The following assessments will be performed at during the remaining visits (Day 8 and 15) in the first treatment cycle:

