6.1.4. Leronlimab (PRO 140) - Post Injection Monitoring

Subject will be observed at approximately 30 minutes post-injection or longer if necessary for injection site reaction as per CTCAE v5.0.

In addition, the tolerability of repeated subcutaneous administration of PRO 140 is evaluated based on assessment of subject-perceived injection site pain using the Pain Visual Analog Scale (VAS).

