The grading for all subjects and parameters will be listed. The number and percentage of patients with worst reported DAIDS grade will be summarized regardless of the location of injection (i.e., left or right side) in the abdomen. Each patient will be counted only for the worst grade observed.

In addition, time to onset of the first worst case injection site reaction will be summarized.

Time to onset of worst grade will be summarized for each local injection reaction parameter listed above using Kaplan-Meier method. Median time to onset and 95% C.I will be summarized. In addition, Kaplan-Meier plots will be generated.

8.4.2.2 Systemic manifestations (e.g., hypotension, fever, difficulty breathing) within the post-administration monitoring period

This will be assessed from the vital signs data using the pre and post assessment:

- Hypotension if there is a reduction in SBP of >= 20 mmHg or reduction in DBP of >= 10 mmHg or if post treatment SBP is >= 90mmHg or DBP is <=60mmHg
- Fever if post treatment temperature is $> 40^{\circ}$ C
- Difficulty breathing if increase in Respiratory Rate is > 30%

The subjects with above systemic manifestations will be listed. Shift table for Fever will be presented with counts and percentages of subjects for shift (change) from pre-treatment at T1 to post-treatment at T1. Percentage of subjects with Hypotension or Difficulty breathing post treatment will be summarized.

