Carboplatin administration [17]			Х			X			X				
Post Injection Site Evaluation by Investigator [18]			Х	Х	Х	Х	Х	Х	Х	X	Х		
Injection Site Pain Assessment (VAS) [19]				X	X	X	X	X	X	X	X		
Survival status												X	X[20]
Concomitant medications	Х	Х	Х	Х	Х	Х	Х	Х	Х	Х	Х	Х	X[23]
Adverse Events			Х	Х	Х	X	Х	Х	X	Х	Х	Х	

Footnotes

- [1] A separate Informed Consent Form (ICF) will be used for the pre-screening. The pre-screening period is designed for evaluation of histologically confirmed diagnosis of TN MBC (documented by HER-2 negative, ER<1%, PR<1%) and CCR5 positive status by Immunohistochemistry (IHC) assay. This assay will be performed in archival tissue from previous biopsy specimens. If archival tissue is not available then, fresh core or excisional biopsy will be done. If patient qualifies, then they will undergo full screening.
- [2] Informed consent must be obtained prior to patient participation in any protocol-related activities that are not part of routine care.
- [3] A complete review of the subject's past medical history, past surgeries, and current therapies (medications and non-medications) will be undertaken by the Investigator to check that all inclusion and no exclusion criteria have been met.
- [4] Vital signs include blood pressure, heart rate, respiration rate, and temperature.
- [5] Weight only
- [6] Symptom-directed physical examination

- [7] A 12-lead EKG will be repeated during the study only if clinically indicated and at the discretion of the treating physician.
- [8] Scans are to be done at the end of 2 cycles (prior to cycle 3) for the first 13 months and at end of 3 cycles (9 weeks) thereafter, and at End of Treatment (EOT) visit by CT, PET/CT or MRI with contrast (per treating investigator's discretion) using the same method as at baseline. Tumor measurements will be done using RECIST1.1. To be assigned a status of PR or CR, changes in tumor measurements must be confirmed by repeat assessments that should be performed 6 weeks after the criteria for response are first met. In the case of SD, measurements must have met the SD criteria at least once after study entry at a minimum interval of 6 weeks.
- [9] Hemoglobin, Hematocrit (HCT), Red Blood Cells (RBC), White Blood Cells (WBC) with total and differential count, absolute lymphocyte count, absolute neutrophil count (ANC) and platelets.
- [10] Serum Biochemistry will include:

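### SAP 8.4.2.2 needs a post-dose vital-signs reading, and a visit called T1, that neither document schedules

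*SAP*

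**What the plan says.** SAP 8.4.2.2 covers systemic manifestations in the monitoring period that follows administration. On the data source it says: "This will be assessed from the vital signs data using the pre and post assessment". Hypotension is flagged from a fall in blood pressure or from the post-treatment level, fever from the post-treatment temperature, and difficulty breathing from a rise in respiratory rate. Three outputs follow: a listing of affected subjects, a fever shift table running "from pre-treatment at T1 to post-treatment at T1", and percentages with hypotension or difficulty breathing.

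The collection side is in the protocol. Table 4-1, footnote 4, reads: "Vital signs include blood pressure, heart rate, respiration rate, and temperature will be measured at clinic visit". The matching footnote in SAP Appendix 1 (Figure 9-1) names the parameters and gives no timing: "Vital signs include blood pressure, heart rate, respiration rate, and temperature". Protocol Section 4 (Treatment Period) includes "physical examination, vital signs and documentation of ECOG performance status" among the assessments to be finished before treatment is given. Protocol 6.1.4 describes what happens after the injection: "Subject will be observed at approximately 30 minutes post-injection or longer if necessary for injection site reaction as per CTCAE v5.0".

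**The concern.** The SAP specifies an analysis whose input the protocol does not ask sites to collect. Every criterion in 8.4.2.2 uses a post-dose value, and the changes in blood pressure and respiratory rate also need a pre-dose value from the same occasion. T1 matches no visit in either schedule, where visits are labelled C1D1, C1D8 and so on.

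What is at stake is how one set of safety outputs will be read. Allergic and flu-like reactions are the first risk the protocol describes (1.6.1), and safety and tolerability belong to the Phase Ib primary objective (Section 2). A section headed as a post-injection assessment, with nothing in its listing, invites the conclusion that no reactions occurred, when in fact no post-injection readings were scheduled.

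**Working it through.** The plan gives no figure to reproduce. The check sets what the analysis needs against each instruction that could supply it.

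**What the analysis needs.** Two vital-signs sets around one injection, the second inside the monitoring period (about 30 minutes under Protocol 6.1.4 and 7.13).

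**What is scheduled.**

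| Place | Content on vital signs |
|---|---|
| Protocol Table 4-1; SAP Figure 9-1 | One row, one mark per visit, no pre/post split |
| Protocol Section 4, Treatment Period | Among the assessments completed before treatment |
| Protocol 4.3.1 (C1D1) | "Vital Signs and body weight measurement" appears once, ahead of both drugs; the items after dosing are injection-site evaluation, toxicity assessment and adverse-event review |
| Protocol 4.3.2 (C1D8, C1D15) | Listed once, ahead of leronlimab |
| Protocol 6.1.4, 7.13 | Post-injection observation is for injection-site reaction; no vital signs |
| Protocol 7.6 | Parameters and seated rest; no timing relative to dose |
| Note closing Protocol 4.3, home dosing | Vital signs not applicable |
| Protocol 4.5, unscheduled visits | At the investigator's discretion; not a planned set |

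For contrast, Protocol 7.14 asks for the injection-site pain scale before and immediately after each dose, while Table 4-1 footnote 20 mentions only the pre-dose reading. Both state timing relative to the dose. The vital-signs entries in the schedules and in 7.6 do not.

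**Pairs available.**
- Clinic dose: 1 scheduled set against 2 needed, so 0 pairs.
- Home dose (Day 8 or Day 15 after Cycle 1): 0 scheduled sets, so 0 pairs.

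**Time from an injection to the next scheduled reading.**
- Consecutive clinic visits, window 7 ± 1 days: 7 − 1 = 6 to 7 + 1 = 8 days.
- Day 1 of a later cycle to the next Day 1, with Days 8 and 15 at home: three such intervals, 3 × 6 = 18 to 3 × 8 = 24 days. The cycle length of 21 ± 3 days in the note to Protocol Figure 3-1 gives the same range.
- Last treatment visit to End of Treatment, 30 ± 3 days: 27 to 33 days.

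None of these falls within a 30-minute observation.

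**The T1 table.** The SAP describes it as "for shift (change) from pre-treatment at T1 to post-treatment at T1". Both readings must come from one visit. No visit carries that name, and no visit has a second scheduled set.

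**The case against.** The strongest reply is that little depends on this output, and that systemic reactions are looked for elsewhere. That is largely right. Adverse events are elicited by direct questioning (Protocol 9.1), and toxicity and adverse-event review close the C1D1 list. An anaphylactic reaction is a DLT and a trigger for DSMB review. SAP 8.4.2.3 summarises local, systemic, hypersensitivity and anaphylactic reactions from adverse-event data, and SAP 8.4.4.1 and 8.4.4.2 flag notable vital signs. The Phase Ib primary outcome is the MTD by DLTs, and no DLT uses the pre/post comparison. A reader might infer that systemic reactions will go undetected; the documents do not support that.

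Two other stronger readings also fail. A reader might infer that analysts will pair each pre-dose set with the next visit's set. The heading of 8.4.2.2 confines the analysis to the monitoring period and the fever shift is within one visit, so nothing permits that pairing. A reader might also infer that a rate of zero will be reported. SAP 7.3 bars imputation and restricts summaries to observed data, so the correct display is no evaluable pairs. The risk that remains is misreading, not a false rate written into the plan.

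The evidence has limits too. No sentence says that only one set is taken; this is inferred from the single row, the single listing and the missing timing. Section 4 states what must be done before treatment and does not forbid a later reading. The list in Protocol 4.3.3 and the start of 4.3.4 are incomplete in the copy reviewed, so the point rests on the two schedules and the intact Cycle 1 lists. The eCRF is not among the documents and may hold pre/post fields. Sites may also take readings on their own initiative, but these would be unscheduled and unstandardised. None of this supplies the missing instruction.

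**Conclusion.** The point holds as an inconsistency between the SAP and the protocol. The pre/post analysis in SAP 8.4.2.2 cannot be run from scheduled data: there are 0 scheduled evaluable pairs, the nearest later reading is at least 6 days away, and T1 is undefined. The affected outputs are the systemic-manifestation listing, the fever shift table, and the hypotension and breathing percentages. Safety reporting here is descriptive (SAP 8.4), and dose escalation, the MTD and the efficacy results are untouched.

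This assumes that sites follow the schedule as written and that the eCRF adds no post-dose set. It is separate from any question about the cut-offs used in the same section.

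**What to change.** Reconcile the two documents in one of two ways.

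1. **Collect the reading.** Add one timed set (blood pressure, temperature, respiratory rate) at the existing 30-minute observation for clinic-administered doses, at least C1D1, C1D8 and C1D15. Put it in Protocol 4.3.1, 4.3.2, 6.1.4 and Table 4-1, and replace T1 in SAP 8.4.2.2 with those visits. C1D8 and C1D15 are especially informative because no carboplatin is given on those days. The cost is a protocol amendment with IRB approval (Protocol 11.3), a few minutes per visit and a CRF field. It cannot recover doses already given, and the documents do not state enrolment status.

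2. **Drop the analysis.** Delete the pre/post comparison and the T1 table, and report these events from adverse-event data under SAP 8.4.2.3. This costs essentially nothing beyond a text change. It does need one repair: 8.4.2.3 takes its list of organ classes and preferred terms from Section 10.1, but SAP Section 10 is the 3+3 design figure, so the list must be supplied or the reference corrected.

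If neither is done before reporting, the outputs should state that no post-injection vital signs were scheduled.

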8.4.4 Vital Signs

Vital sign assessments are performed in order to characterize basic body function. The parameters collected in this study are: systolic BP (mmHg), diastolic BP (mmHg), temperature (0C), heart rate (bpm), respiratory rate (rpm).

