8.4.4.1 Clinically notable elevated values

- Systolic BP: \geq 160 mmHg and an increase \geq 20 mmHg from baseline
- Diastolic BP: ≥ 100 mmHg and an increase ≥ 15 mmHg from baseline.
- Body temperature: ≥ 39.1 °C
- Heart rate: ≥ 120 bpm with increase from baseline of ≥ 15 bpm
- Respiration rate: ≥ 24 breaths per minute with increase from baseline of ≥ 6 breaths per

minute

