8.4.4.2 Clinically notable below normal values

• Systolic BP: \leq 90 mmHg and a decrease \geq 20 mmHg from baseline

• Diastolic BP: ≤ 50 mmHg and a decrease ≥ 15 mmHg from baseline

• Body temperature: ≤ 35°C

• Heart rate: ≤ 50 bpm with decrease from baseline of ≥ 15 bpm

 Respiration rate: < 8 breaths per minute with decrease from baseline of ≥ 6 breaths per minute

Number and percentage of patients with at least one post-baseline vital sign abnormality (in both directions, i.e. both elevated and below normal values) will be summarized by treatment group.

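### The SAP's post-injection fever flag (above 40 °C) is less sensitive than its own clinically notable limit (39.1 °C), so readings of 39.1 to 40.0 °C are left out of the fever display

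*SAP*

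**What the plan says.** SAP 8.4.2.2 covers systemic manifestations in the monitoring period after administration: hypotension, fever and difficulty breathing. On the data source it says "This will be assessed from the vital signs data using the pre and post assessment". The fever rule reads "Fever if post treatment temperature is" above 40 °C. Two outputs use it. Subjects with any of the three manifestations are listed, and "Shift table for Fever will be presented with counts and percentages of subjects for shift (change) from pre-treatment at T1 to post-treatment at T1".

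SAP 8.4.4 deals with vital signs in general: "The parameters collected in this study are: systolic BP (mmHg), diastolic BP (mmHg), temperature (0C), heart rate (bpm), respiratory rate (rpm"). Under clinically notable elevated values, 8.4.4.1 sets "Body temperature: ≥ 39.1 °C". The output, described at the end of 8.4.4.2, is "Number and percentage of patients with at least one post-baseline vital sign abnormality", in either direction, by treatment group.

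Neither section refers to the other. Protocol 1.6.1 names fever among the flu-like reactions sometimes seen with monoclonal antibodies, and the DLT list includes neutropenic fever, but neither place gives a temperature. SAP 2.5 and protocol 8.7.3.2 state that toxicities and adverse events are graded by CTCAE v5.0.

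**The concern.** One would expect a flag aimed at a particular reaction, in a short window after an injection, to be at least as sensitive as a general screen of all post-baseline values. Here the order is reversed: the SAP calls a temperature clinically notable 0.9 °C before it will call it fever.

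At stake is how the fever listing and shift table are read. They are the SAP's vital-sign displays of fever tied to the injection. If they show few or no fevers, a reader cannot tell whether temperatures stayed low or whether the cut-off removed them. Fever is a reaction that the protocol itself anticipates for this class of drug.

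**Working it through.** **Inputs.**

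- Fever rule F: T > 40 °C, strict inequality, absolute value (SAP 8.4.2.2).
- Notable rule N: T ≥ 39.1 °C, absolute value (SAP 8.4.4.1).
- Both use temperature in °C from the vital signs data (SAP 8.4.2.2 and 8.4.4). Neither has a change-from-baseline condition.
- Assumption: readings are recorded to 0.1 °C. The documents do not state the precision.

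The plan gives no figure to reproduce, so the check compares the two rules directly.

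**Step 1: readings that are notable but not fever.** N and not F means 39.1 ≤ T ≤ 40.0. The upper end is included because 40.0 is not greater than 40. In steps of 0.1 °C this is (40.0 − 39.1)/0.1 + 1 = 10 values. The gap between the limits is 40.0 − 39.1 = 0.9 °C.

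**Step 2: readings that are fever but not notable.** T > 40 implies T ≥ 39.1, so there are none. The fever rule is strictly the narrower of the two.

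**Step 3: follow one reading, 39.8 °C after an injection, through the planned outputs.**

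| Output | Rule | Result |
|---|---|---|
| SAP 8.4.2.2 listing | T > 40 | not listed as fever |
| SAP 8.4.2.2 shift table, T1 | T > 40 | no shift to fever |
| SAP 8.4.4 summary | T ≥ 39.1 | subject counted as having a vital sign abnormality |
| SAP 8 data listings | none | value shown |
| SAP 8.4.1 and 8.4.2.3 adverse event tables | investigator report | appears if reported; in 8.4.2.3 only if related to the injection |

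**Step 4: compare the other limits in the same list.**

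- *Blood pressure.* SAP 8.4.2.2 flags a fall of at least 20 mmHg systolic or 10 mmHg diastolic. SAP 8.4.4.2 requires a fall of at least 20 systolic or 15 diastolic together with a low absolute value. Where the pre-dose reading is the baseline, every notable low pressure is therefore also flagged as hypotension: the post-injection rule is the wider one, the opposite of what is done for temperature.
- *Systolic level.* SAP 8.4.2.2 also flags hypotension if post-treatment systolic pressure is at or above 90 mmHg, whereas 8.4.4.2 uses at or below 90 mmHg. The direction appears reversed, and as written it would flag nearly everyone.
- *Breathing.* SAP 8.4.2.2 needs a rise of more than 30%; 8.4.4.1 needs at least 24 breaths per minute and a rise of at least 6. Going from 20 to 26 is a rise of 6, and 6/20 = 30%, so it is notable but not flagged.

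**The case against.** **Different outputs over different windows.** SAP 8.4.2.2 concerns the period after administration and 8.4.4 any post-baseline value, and nothing in the SAP requires fever and notable to coincide. That stands, so this is not a strict logical contradiction. It does not explain why the injection-specific flag should be the less sensitive one, and the SAP offers no reason.

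**Nothing is lost.** Readings of 39.1 to 40.0 °C stay in the 8.4.4 summary and the listings. A fever that the investigator reports is summarised in 8.4.1 and, if related to the injection, in 8.4.2.3. This also stands, and it confines the defect to the fever part of the 8.4.2.2 listing and the T1 shift table. The 8.4.4 summary is not a substitute, because it does not tie a reading to an injection.

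**There may be few readings to misclassify.** The protocol's schedule (Table 4-1) and its vital signs section (7.6) give no post-injection time point for vital signs. The 30-minute observation in 6.1.4 is for injection site reactions. Vital signs do not apply to doses given at home, and T1 is not defined in the SAP text. This is a fair limit on the practical size. It leaves the rule as it is wherever a post-treatment reading exists.

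**Stronger readings that the documents do not support.** A reader might infer that the table will miss most systemic reactions. No temperature distribution is given, and the combined listing would over-flag through the hypotension rule. A reader might also say that fevers below 39.1 °C are missed, but the documents give no lower definition of fever against which to judge that. Finally, a reader might raise the stakes by calling this a first combination study. The protocol does not say so, and it describes earlier use of the antibody alongside antiretroviral therapy in the CD02 study.

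**Conclusion.** The point holds as a minor inconsistency in safety reporting. Under the SAP as written, every post-treatment temperature from 39.1 to 40.0 °C inclusive is clinically notable in one output and not fever in the output meant to show systemic reactions to injection. Post-injection fever is understated there to the extent that such readings occur, and the documents do not allow that extent to be estimated.

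The conclusion rests only on the two stated limits and on their applying to the same temperature variable. The effect is descriptive: SAP 8.4 plans no inferential safety statistics. PFS and sample size are untouched, as are the DLT and MTD rules, where neutropenic fever is a separate item. The documents do not show which limit was intended. The apparently reversed systolic limit in the same list makes an unchecked entry a plausible explanation, but does not prove it.

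**What to change.** Reconcile the two analysis limits so that the 8.4.2.2 fever flag is no less sensitive than the SAP's own notable limit. Either of these would do:

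- use the 8.4.4.1 limit in both sections; or
- tabulate post-injection fever by the CTCAE v5.0 grading already adopted for adverse events. The protocol reproduces only the general grade descriptions and a link, so the sponsor should confirm from the source that the lowest fever grade starts no higher than 39.1 °C.

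If the difference is deliberate, the SAP should state the reason and note under the fever displays that readings of 39.1 to 40.0 °C are reported elsewhere.

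In the same edit, check the other 8.4.2.2 limits against 8.4.4, above all the direction of the systolic limit at 90 mmHg. It would also help to define T1 and say which reading counts as post-treatment.

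The cost is one line for temperature and a few more for the rest of the list. It needs no new data and no change to trial conduct.
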